8.2 Data Analysis

8.2.1. Aim 1 (Survey)

8.2.1.1. Estimate the prevalence of HPV vaccine initiation in cancer survivors ages 9 to 26 years. Examine the sociodemographic, behavioral, and medical determinants of HPV vaccine non-initiation

The outcome is HPV vaccine initiation status (Yes: received at least one dose/ No: never received any doses) at the time of survey completion. The prevalence (p) of qHPV vaccine initiation among 981 survey participants and its 2-sided 95% CI will be calculated. A one-sided t-test of $H_0: p \leq 0.4$ will be conducted using Type I error=0.05. Significant predictors of vaccine initiation will be identified using logistic regression. We will consider predictors relevant to vaccine acceptance or refusal, including sociodemographic (e.g., age, sex, education, race/ethnicity, income), medical (e.g., cancer diagnosis, intensity of treatment, conventional treatment vs. HCT), and behavioral (e.g., perceived susceptibility to HPV, perceived severity of consequences of HPV infection, attitudes toward vaccination, attitudes toward healthcare provider recommendation of vaccine, engagement in health promotion behaviors, knowledge regarding association of HPV with cancer, familial decision-making style). A sample size of 981 will provide 80% power at 5% significance level to detect an odds ratio of 1.45 to 2.0 for a dichotomous variable with 50% of the sample in one group.

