Cancer diagnosis and treatment history: Patients who have received more therapy that is immunosuppressive may experience a prolonged recovery period. Patients with hematological malignancies are more likely to require more intense therapies, including allogeneic HCT, which may result in chronic GvHD requiring ongoing immunosuppression.¹¹⁶ Thus, cancer diagnosis and treatment-related factors may play a significant role in decisions related to vaccine initiation in the cancer survivor population; there is currently very little data to support this, resulting in a critical gap in the literature that this study will address.

2.8 **Theoretical Model/Conceptual Framework**

An integrative framework guided by the Health Belief Model (HBM),^{117,118} and Theory of Planned Behavior (TPB),¹¹⁹ will provide the theoretical basis for testing our predictive models of HPV vaccination initiation and intent. The HBM postulates that a health behavior (e.g., initiating HPV vaccination) is influenced by perceptions of both the threat posed by a health problem (e.g., HPV-related cancers) and the value of actions aimed at reducing the threat (e.g., HPV vaccination as a means of reducing risk of HPV-related cancers). The HBM includes 6 primary factors (perceived susceptibility, severity, barriers, benefits, cues to action, and self efficacy)¹¹⁸ that explain a significant proportion of the variance regarding decision to engage in a health-promoting behavior. TPB posits that an individual's attitudes regarding a behavior, perceptions of the beliefs of significant others (norms), and perceived control over a behavior influence behavioral intent, which in turn drives engagement in the actual behavior.¹¹⁹ This theory assumes that behavioral intention is the most significant determinant of engaging in a behavior,

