with intent initially influenced by personal evaluation of a behavior and personal beliefs regarding whether important people would approve or disapprove of the behavior.¹²⁰ Thus, multiple factors influence HPV vaccine intent, which subsequently predicts initiation of HPV vaccine. In this aim, the primary dependent variable will be HPV vaccine non-initiation prior to study participation; by collecting survey data regarding vaccine intention and key factors influencing health behaviors informed through HBM and TPB (Table 1), we will identify potentially modifiable barriers to HPV vaccine initiation in cancer survivors, setting the stage for development of interventions to improve uptake of the HPV vaccine in this vulnerable population.

Table 1. Theoretical Basis for Testing Predictive Model

PROPOSED PREDICTORS OF HPV VACCINE INITIATION	SURVEY ITEMS ELICITING PREDICTORS
†Perceived susceptibility to HPV-related disease	D1a-e
†Perceived severity of HPV-related disease	D2a-h
†Perceived barriers to HPV vaccination	D3a-l
†Perceived benefits/efficacy of the HPV vaccine	D4a-g
†Cues to action	C1, C2a-m
†Self-efficacy	D5a-f, D6
Knowledge of HPV and related health risks	B1-10
Health behaviors	G1-17
Demographic factors	A1-9
Sexual relationships/communication	H1a-t; I1-5; J1-13
§Attitude toward vaccine-related decision-making	C6-10; F1a-j
§Social and environmental influences on decision	E1a-q, E2-3
§Healthcare provider recommendation	C2c,d; E1a; G6,8,18
§Intention to vaccinate	C5a-d
OUTCOME OF INTEREST: HPV VACCINE INITIATION	
Vaccination status	C3-4

†Component of Health Belief Model §Component of Theory of Planned Behavior

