4.3 Data Abstraction

The *Medical Record Review Form* and *Intensity of Treatment Rating Scale 2.0* will be completed for all patients enrolled in Aim 1 (Survey).

Medical Record Review Form: This form captures data elements abstracted from the medical record, including diagnosis, date of birth, date of diagnosis, time from diagnosis, treatment modalities (surgery, chemotherapy, radiation, HCT), and date of treatment completion (see Appendix 1).

Intensity of Treatment Rating Scale 2.0 (ITR-2): The ITR-2¹²¹ (see Appendix 2) is a validated tool that uses cancer diagnosis, stage or risk level, and treatment modalities to produce an overall rating of cancer treatment intensity with 4 levels (least to most intensive); inter-rater reliability of this tool is .87.

The two instruments provide a concise record of the diagnosis and treatment intensity. Ten percent of randomly selected records will be rated independently by two reviewers to establish inter-rater reliability.

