4.4.6. Current Vaccination Status (Primary Dependent Variable)

The patient's HPV vaccination status is determined by one item, the dependent variable for Primary Aim #1. The item reads "Have you (your son/daughter) received the HPV vaccination?" Brand name prompts (Gardasil – males and females, and Cervarix – females only) are included in the item.

Response choices include 4 options: “I (my son/daughter) have received... A) 0 of the 3 shot series (has not started the vaccine, B) 1 of the 3 shot series, C) 2 of the 3 shot series, and D) 3 of the 3 shot series (has completed the vaccine).” Responses will be dichotomized to reflect those who have and have not initiated HPV vaccination. An additional item for those who indicate prior initiation of the HPV vaccine series captures the age of the patient at the time of the first HPV vaccine dose.

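### Aim 1 regresses ever-vaccinated status on cancer diagnosis and treatment without setting aside doses given before diagnosis, which those factors cannot have influenced

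*Combined protocol and SAP*

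**What the plan says.** Section 8.2.1.1 sets the outcome: "The outcome is HPV vaccine initiation status (Yes: received at least one dose/ No: never received any doses) at the time of survey completion". Section 2.8 anchors it only to study entry: "the primary dependent variable will be HPV vaccine non-initiation prior to study participation". Section 4.4.6 codes the survey item to match: "Responses will be dichotomized to reflect those who have and have not initiated HPV vaccination".

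Logistic regression on this outcome is to identify significant predictors. One of the three predictor classes is "medical (e.g., cancer diagnosis, intensity of treatment, conventional treatment vs. HCT"). Aim 1a calls these factors determinants of non-initiation, and section 2.7.3 explains why they are of interest: "cancer diagnosis and treatment-related factors may play a significant role in decisions related to vaccine initiation in the cancer survivor population".

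The dates needed to order the events are collected. For initiators, a further survey item "captures the age of the patient at the time of the first HPV vaccine dose". The record review in section 4.3 abstracts items "including diagnosis, date of birth, date of diagnosis, time from diagnosis, treatment modalities" and the date of treatment completion. Neither the Aim 1 eligibility criteria (section 3.1) nor the analysis section separates doses given before diagnosis from later ones, whether by exclusion, stratification, time-to-event analysis or sensitivity analysis.

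**The concern.** The medical predictors are fixed at or after diagnosis, while the outcome counts any dose at any earlier age. A participant vaccinated, later diagnosed and later surveyed enters the model as an initiator whose status is to be explained by a diagnosis and treatment that had not yet happened.

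The rationale in the Abstract and section 2.7.3 concerns decisions taken once the person has had cancer: reluctance of families or clinicians, and the influence of treatment history. Doses before diagnosis carry no information on that. If they are equally common across treatment groups, they dilute a real association. If they differ, for example because one group was diagnosed at younger ages, they can distort it. Section 2.10.2 intends to use the results to pick subgroups for targeted interventions, so a misread treatment coefficient would have consequences.

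**Working it through.** **Inputs from the documents.** 981 participants, 80% power, 5% level, detectable odds ratio (OR) 1.45 to 2.0 for a 50:50 covariate (8.2.1.1). General-population and planning rate 40% (1.0, 8.1). Pilot rate 33.3% (2.9). HCT share 411/2161 = 19.0% (Table 2). Licensure from age 9, females 2006 and males 2009 (Abstract). Aim 1 enrollment closed by 17 August 2015 (3.1).

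**Assumed, because the documents give no figure.** The share vaccinated before diagnosis, s; initiation after diagnosis among those still unvaccinated, q, at 20% after HCT and 35% after conventional therapy; therapy lasting 0.5 to 3 years.

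**1. The plan's own figure.** With n = 981/2 = 490.5 per group and two-sided 5%, power = Φ{[|p1 − p0| − 1.96·√(2p̄(1 − p̄)/n)] / √([p0(1 − p0) + p1(1 − p1)]/n)}. At p0 = 0.333 and p1 = 0.4196 this is Φ{(0.0866 − 0.0606)/0.0308} = Φ(0.84) = 80%, and OR = (0.4196/0.5804)/(0.333/0.667) = 1.45. At p0 = 0.05 and p1 = 0.0966, power is again 80% and OR = 2.03. The stated range is reproduced for reference rates of about 5% to 33%.

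**2. Balanced doses before diagnosis.** Ever-vaccinated probability is p = s + (1 − s)q. The overall rate weights the two groups by the 19.0% HCT share.

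| s | HCT | Conventional | OR | Overall initiation |
|---|---|---|---|---|
| 0 | 0.200 | 0.350 | 0.46 | 32.1% |
| 5% | 0.240 | 0.3825 | 0.51 | 35.5% |
| 10% | 0.280 | 0.415 | 0.55 | 38.9% |
| 15% | 0.320 | 0.4475 | 0.58 | 42.3% |
| 20% | 0.360 | 0.480 | 0.61 | 45.7% |

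For s = 10%: (0.28/0.72)/(0.415/0.585) = 0.389/0.709 = 0.55. The last two rows exceed both the 40% planning rate and the pilot rate, so only 5% and 10% are used below.

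**3. Effect at the plan's detectable OR.** Hold overall initiation at 40%, set the true post-diagnosis OR to 1.45, and let a fraction f of all initiations predate diagnosis, so that s = 0.40f in both groups.

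| f | s | Ever/never OR | Power, n = 981 | Unvaccinated at diagnosis | Power for OR 1.45 |
|---|---|---|---|---|---|
| 0 | 0 | 1.45 | 81% | 981 | 81% |
| 10% | 4% | 1.42 | 76% | 941 | 79% |
| 25% | 10% | 1.36 | 66% | 882 | 74% |

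For f = 25% the ever-vaccinated rates are 0.363 and 0.437, and (0.437/0.563)/(0.363/0.637) = 1.36. The restricted model has fewer people but more power, because its OR is not diluted.

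**4. Unbalanced doses, direction only.** Take q = 25% in both groups, so there is no effect after diagnosis, with s = 5% after HCT and 15% or 20% after conventional therapy. The ever-vaccinated rates are 0.2875 against 0.3625 or 0.40, and the crude OR is 0.71 or 0.61.

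**5. Calendar limit.** Therapy of 0.5 to 3 years plus 12 to 60 months off therapy puts diagnosis 0.5 + 1 = 1.5 to 3 + 5 = 8 years before the survey. For a survey at closure, that is about 2007 to early 2014. A male diagnosed before 2009 had no licensed vaccine before diagnosis. Earlier surveys move the diagnosis window further back.

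**The case against.** The strongest reply is that ever/never is deliberate. The aim is to find subgroups with low coverage, Aim 1 also finds unimmunized people for Aim 2, and the 40% benchmark is not restricted by timing. For deciding who is unprotected today, the date of an earlier dose does not matter. This stands for the prevalence estimate and for sociodemographic predictors. A reader might infer that the prevalence overstates uptake after cancer, but the plan never claims to estimate that quantity, so this is not an error. The reply does not cover factors presented as determinants of the vaccination decision.

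Second, age and sex are already listed as predictors, and the 12-60 month window makes age at survey track age at diagnosis. Adjustment should therefore remove much of the distortion in step 4. Those odds ratios are crude, their 5% versus 15-20% gap is invented, and they should not be read as the expected bias. Adjustment does not take pre-diagnosis doses out of the outcome, so the dilution remains.

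Third, a reader might infer that many participants, or everyone aged 17 or over, could have been vaccinated before diagnosis. Being 9 or older at diagnosis is not enough: the vaccine also had to be licensed for that sex, and males are 1221/2161 = 56.5% of the eligible pool. The documents support only that such doses were possible for part of the cohort.

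Finally, a cross-sectional survey always leaves temporal order uncertain. That is fair for beliefs measured at the survey. Here the order can largely be recovered from collected dates.

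**Conclusion.** The point holds for the diagnosis, treatment-intensity and HCT predictors in Aim 1a. The plan lets doses that these factors could not have influenced enter their odds ratios, and it has no rule to separate them. The prevalence estimate, the comparison with 40%, and fixed factors such as sex and race are unaffected.

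The true size is unknown because the pre-diagnosis share is not in the documents. With 5-10% assumed in both groups, which keeps overall initiation at or below 40%, an OR of 0.46 becomes 0.51-0.55. At the plan's smallest detectable OR, 1.45 becomes 1.42 or 1.36, and power falls from 81% to 76% or 66%, if 10% or 25% of initiations predate diagnosis. Those power figures assume a 50:50 covariate. At a 19% share, power for the HCT contrast would be lower throughout. The dilution is moderate; the change is worth making because it bears on a stated sub-aim and needs no new data.

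**What to change.** Amend section 8.2.1.1 as follows.

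- Keep ever-initiated as the outcome for prevalence and for the sociodemographic predictors.
- Use age at first dose, date of birth and date of diagnosis to classify each initiator as before or after diagnosis, and report the split.
- For diagnosis and treatment predictors, fit the model among participants unvaccinated at diagnosis, with initiation after diagnosis as the outcome. Adjust for age, sex and time since the later of diagnosis or vaccine eligibility (age 9 and licensure for that sex). Without the last term, unequal opportunity to be vaccinated would remain.
- Where age at first dose equals age at diagnosis, run the model both ways.
- Repeat with the anchor moved to treatment completion, so that doses given during therapy or before HCT do not precede the predictors they are related to.

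The cost is analysis wording and programming; closed enrollment is no obstacle. This model loses some sample (882 of 981 remain if 25% of initiations at a 40% overall rate predate diagnosis). It also relies on the patient's or parent's report of age at first dose, which will leave ties if it is recorded in whole years.

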8.2.2. Aim 2 (Vaccine Evaluation)

8.2.2.1. Determine immunogenicity of qHPV and 9vHPV vaccine 1 month following the third and final vaccine dose

The primary analytic approach will be per-protocol (PP)³⁰ analysis; intention to treat analysis will also be conducted. The evaluation will be completed separately for the qHPV and 9vHPV cohorts. The sample size is powered to determine whether vaccine-induced anti-HPV-16 and -18 neutralizing antibody response in cancer survivors is comparable to the age- and sex-matched general population (Table 7); PP immunogenicity population includes participants who are seronegative for the oncogenic vaccine components of primary interest (HPV-16, -18) on Day 1, complete all three vaccine doses within the protocol-specified time frames, and have immunogenicity data available at the time of analysis. Each vaccine component will be analyzed separately, and we will adjust for intensity of treatment. Anti-HPV-6 and -11 (and in the 9vHPV cohort, Anti-HPV-31, -33, -45, -52, and -58) response will also be explored. The primary outcome of interest is GMT. We will also assess seropositivity rates among cancer survivors. Seropositivity (binary variable) is defined as: qHPV cohort: Anti-HPV-6, -11, -16, and -18 titer ≥ 20 , 16, 20, and 24 mMU/ml respectively;³⁰ 9vHPV cohort: Anti-HPV-6, -11, -16, -18, -31, -33, -45, -52, and -58 titer ≥ 30 , 16, 20, 24, 10, 8, 8, 8, and 8 mMU/ml, respectively.⁶⁹

Outcome measure (GMT): Using the historical healthy population for qHPV²⁸ and 9vHPV⁶⁹ respectively, a multiplicity-adjusted 95% 2-sided confidence intervals for the ratio of mean GMT for HPV-16 and -18 in the cancer and healthy population will be computed. If the lower 95% limit is greater than 0.5, immunogenicity in cancer survivors will be considered non-inferior.³⁰

Outcome measure: (seropositivity) [Exploratory only; study is not powered for this]: The percent of seropositive participants at Month 7 will be compared to the percent of age- and sex-matched seroconverted individuals in the historical healthy population for each of 2 vaccine components. Two one-sided tests of noninferiority (for each of 2 HPV types) will be conducted for each age-sex group at the 0.025 level (multiplicity adjusted) according to the methods of Miettinen and Nurminen.¹³⁷ Seroconversion in cancer survivors will be considered non-inferior if the lower 95% CI for the difference in percent seropositive between the healthy and cancer population is <5 percentage points.³⁰ The above analyses will be conducted for PP and IT samples. Although not powered to detect non-inferiority for HPV-6 and -11 (and in the 9vHPV cohort, HPV-31, -33, -45, -52, and -58), we will also conduct similar analyses for GMT and seropositivity for these types.

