1.0 OBJECTIVES AND HYPOTHESES

Aim 1:

Using a cross-sectional survey approach, estimate the prevalence of HPV vaccine non-initiation

- a. Examine sociodemographic, behavioral, and medical determinants of HPV vaccine non-initiation

Hypothesis 1: The HPV vaccine initiation rates for cancer survivors will be less than 40% (estimated rate in the general population); subgroups of cancer survivors with particularly low vaccine initiation rates will be identified.

Among cancer survivors identified to be non-immunized in Aim 1, and among additional non-immunized cancer survivors meeting study eligibility criteria:

Aim 2:

Using a single-arm, phase II, open-label, prospective longitudinal trial design, to evaluate the 3-dose qHPV (for patients enrolled on or before 3-1-16) or 9vHPV (for patients enrolled after 3-1-16) vaccine series and measure the following endpoints:

- a. Determine immunogenicity following the third and final vaccine dose
- b. Identify clinical/host factors influencing immunogenicity
- c. Determine the safety/tolerability of the qHPV and 9vHPV vaccine in cancer survivors

Hypothesis 2: Immunogenicity to the qHPV and 9vHPV vaccines will be heterogeneous among cancer survivors, with subpopulations that received the most intense therapy demonstrating inferior immunogenicity. The qHPV and 9vHPV vaccines will be safe and well-tolerated by cancer survivors.

Exploratory sub-aim:

Evaluate the persistence of antibody response at 2 years post vaccine initiation and identify clinical/host factors influencing response persistence.

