8.0 STATISTICAL METHODS

8.1 Sample Size

Aim 1 (Survey): A sample size of 1090 eligible subjects is required to address Specific Aim 1. We have chosen this sample size based on our preliminary study (Section 2.9), from which we can assume that 90% (n=981) of those approached will participate in the survey. A sample of 981 survey participants for Specific Aim 1 will provide 80% power to reject the null hypothesis that the prevalence (p) of HPV vaccine initiation is ≤ 0.4 if the true p is at least 0.44 (one-sided test, Type I error=0.05). It will also provide a 2-sided 95% confidence interval (CI) of sample $p \pm .061$ if true $p=0.4$.

[Protocol v3, 8/17/15: Accrual goal for Aim 1 met, enrollment to survey closed]

Aim 2 (Vaccine Evaluation):

qHPV Vaccine Cohort (patients enrolled on or before 3-1-16): Based on national vaccine initiation rates and our preliminary data (Section 2.9),⁴⁰ we conservatively assume that 60% (n=589) of the 981 survey participants will have not initiated the HPV vaccine. Based on our data (Section 2.9) and prior trials,^{30,31,135} we conservatively assume that of the non-vaccinated survey participants, 60% (n=353) will agree to receive the vaccine, 96% (n=339) will be seronegative at baseline (Intent to Treat [IT] sample), and 92% (n=312) will complete all 3 doses, yielding 312 (Per-Protocol [PP]) subjects who will have received all 3 doses of qHPV vaccine for examining Aim 2.1. This sample size was calculated using the mean GMT and SD reported by Merck & Co.²⁸ for healthy males and females aged 9-15 years and 16-26 years as the historical healthy population. The following assumptions were made: i) cancer survivors were similarly distributed in regard to immunogenicity with the same SD as in this healthy population; ii) margin of equivalence (E) was $\frac{1}{2}$ of the mean GMT of the healthy population (Table 7). Using the method of Korn and Freidlin¹³⁶ for sample size calculations using historical controls, a total of 312 subjects (72 younger females, 77 older females, 82 younger males, and 81 younger males) will provide 80% power to demonstrate non-inferiority with respect to anti-HPV-16, and/or -18 GMT in cancer survivors compared to the healthy population assuming a one-sided t-test, Type I error =0.00312 (for an overall Type I error =0.025), and margin of equivalence (E) shown in Table 7 by sex and age for each vaccine type.

Table 7. Sample Size for Aim 2 (Vaccine Evaluation)

		Females								

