8.2.2.2. Identify clinical/host factors influencing immunogenicity in cancer survivors

Subjects whose GMT at Month 7 is less than ½ of the mean GMT of the corresponding age-sex matched health population will be classified as having lowered immunogenicity. Logistic regression will be used to identify significant predictors of lowered immunogenicity. Potential predictors include sex, primary diagnosis, current age, age at diagnosis/HCT, prior therapy (all therapeutic exposures, including cumulative doses of all immunosuppressive agents), intensity of therapy (conventional therapy vs. HCT), time from completion of therapy, presence/extent of chronic GvHD, dose/duration of immunosuppressive agents post-HCT, and Day 1 Quant Ig. This analysis will be conducted for HPV-16 and -18. At Type I error=0.5,

312 subjects will achieve 80% power to detect odds ratios of 2.0 to 3.2 depending on the hypothesized and true proportions of subjects with lowered immunogenicity (Table 8) or a dichotomized covariate with 50% of the sample in each group.

Table 8. Proportion of Subjects with Lowered Immunogenicity and Associated Odds Ratios

P0	P1	OR
0.05	0.143	3.18
0.1	0.215	2.47
0.2	0.34	2.06
0.3	0.453	1.93
0.4	0.558	1.89
0.5	0.656	1.91
0.6	0.748	1.98

P0 = Hypothesized proportion of subjects with lowered immunogenicity

P1 = True proportion of subjects with lowered immunogenicity

OR = Odds Ratio

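### Section 8.2.2.1 adjusts the comparison with healthy controls for treatment intensity, which those controls do not have, and leaves open the intensity level, mix and scale at which the survivor GMT is read

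*Combined protocol and SAP*

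**What the plan says.** Section 8.2.2.1 describes the per-protocol comparison of survivors with the age- and sex-matched general population. In that paragraph it says "Each vaccine component will be analyzed separately, and we will adjust for intensity of treatment", and shortly afterwards "The primary outcome of interest is GMT". It gives no model, intensity scale, reference level or weighting.

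The next paragraph sets the decision rule. Multiplicity-adjusted "confidence intervals for the ratio of mean GMT for HPV-16 and -18 in the cancer and healthy population will be computed", and "If the lower 95% limit is greater than 0.5, immunogenicity in cancer survivors will be considered non-inferior". The adjustment is not mentioned there.

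The reference consists of published summary figures. Section 8.1 says "This sample size was calculated using the mean GMT and SD reported by Merck & Co", and Table 7 gives those figures by sex and age group only.

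Intensity is defined in two ways. Section 4.3 describes ITR-2, a four-level rating built from diagnosis, stage or risk level, and treatment modality. Section 8.2.2.2 lists "intensity of therapy (conventional therapy vs. HCT") among the predictors of lowered immunogenicity within survivors. Hypothesis 2 in section 1.0 expects heterogeneous immunogenicity, "with subpopulations that received the most intense therapy demonstrating inferior immunogenicity".

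**The concern.** Covariate adjustment of a two-group contrast is useful when the covariate exists in both groups. Treatment intensity has no value in a healthy person, and the reference is a set of stratum means, so nothing on the healthy side can be adjusted. All the adjustment can do is move the survivor GMT to some chosen intensity level or mix. That choice decides which survivors the non-inferiority statement is about, and the plan leaves it open. If intensity matters as Hypothesis 2 expects, one dataset can give several different primary ratios against the same 0.5 limit.

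**Working it through.** **The plan's own figure.** For one sample against a fixed historical mean, with one-sided alpha 0.00312 and 80% power, the noncentral t gives these sample sizes from the Table 7 inputs (HPV-16/HPV-18):

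- younger females 70/68 (stated 72/69)
- older females 79/61 (stated 77/58)
- younger males 71/79 (stated 72/82)
- older males 71/80 (stated 72/81)

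The stratum maxima sum to 70 + 79 + 79 + 80 = 308, against the stated 72 + 77 + 82 + 81 = 312. The alpha is 0.025/8 = 0.003125. The calculation closes to within 3% and contains no intensity covariate.

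**Inputs for the illustration.**

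- f = share with HCT = 411/2161 = 0.19 (Table 2). This is the potentially eligible pool, not the analysed sample; sites range from 0.083 to 0.458.
- k = HCT GMT divided by conventional-therapy GMT. The documents give no value; the range 0.3 to 0.7 is assumed.
- Log SD within level = 0.9, assumed. Table 7 for younger females, HPV-16, has CV = 5585.26/4918.5 = 1.136; if titres are lognormal, the log SD is √ln(1 + 1.136²) = 0.91.
- n = 72 in a stratum, healthy GMT treated as fixed, z = 2.734 for one-sided 0.003125.

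**Effect on the ratio.** On the log scale the all-survivor ratio is R₀ × k^f, where R₀ is the ratio at the conventional-therapy level. Reading at that level therefore multiplies the all-survivor ratio by k^(−f):

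| f | k = 0.7 | k = 0.5 | k = 0.3 |
|---|---|---|---|
| 0.083 | 1.03 | 1.06 | 1.11 |
| 0.19 | 1.07 | 1.14 | 1.26 |
| 0.458 | 1.18 | 1.37 | 1.74 |

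Equal weighting of the two levels gives R₀ × k^0.5, which is below R₀ × k^f whenever f < 0.5 and k < 1. Standardising to the observed mix returns R₀ × k^f, so the point estimate is unchanged.

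**False-pass chance at a true all-survivor ratio of 0.50.** Unadjusted, it is 0.003125, about 0.3%. At the conventional level, 72 × 0.81 = 58.3 patients carry the estimate, so SE = 0.9/√58.3 = 0.118. The chance is P(Z > 2.734 − f·ln(1/k)/SE):

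- k = 0.7: shift 0.068/0.118 = 0.58, chance 1.5%
- k = 0.5: shift 0.132/0.118 = 1.12, chance 5.3%
- k = 0.3: shift 0.229/0.118 = 1.94, chance 21%

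With t in place of the normal distribution, these become about 1.5%, 5% and 20%.

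**Whether the decision can change.** Take R₀ = 0.80, k = 0.3, f = 0.19, so the all-survivor ratio is 0.80 × 0.3^0.19 = 0.636. The unadjusted log SD is √(0.81 + 0.19 × 0.81 × 1.204²) = 1.016.

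| Survivor GMT read at | Ratio | SE (log) | Lower limit | Rule |
|---|---|---|---|---|
| Unadjusted | 0.636 | 0.120 | 0.46 | fails |
| Conventional-therapy level | 0.80 | 0.118 | 0.58 | passes |
| Observed mix | 0.636 | 0.106 | 0.48 | fails |
| Equal weights | 0.44 | 0.135 | 0.30 | fails |

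Using t lowers each limit by less than 0.01. At k = 0.5 with the same R₀, the unadjusted and conventional-level limits (0.52 and 0.58) both pass, while equal weighting (0.39) fails. The choice can therefore turn a fail into a pass or a pass into a fail.

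**The case against.** The strongest reply is that the harmful version is assumed rather than planned. A reader might infer that the adjustment is bound to push the ratio toward non-inferiority. The documents do not support that: no reference level is named, and the direction depends on the choice made. This stands, and it is why the defect is an undefined estimand and not a demonstrated upward bias.

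A reader might also infer that a true ratio of 0.50, read as 0.57 (k = 0.5) or 0.63 (k = 0.3) at the conventional level, already meets the margin. It does not. The rule concerns the lower limit, and with the inputs above the expected lower limits are about 0.41 and 0.46. What rises is the chance of a false pass.

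The link to the decision rule can be questioned as well. The paragraph holding the adjustment sentence also covers exploratory types and seropositivity. The GMT rule, its restatement in section 8.1 and the sample size carry no covariate. Even so, the sentence stands in the survivor-versus-healthy section, and the within-survivor models have their own section with intensity already listed. At best the text permits both readings.

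Finally, the size rests on an assumed k. Section 2.5.2 says that survivors at least a year off therapy mostly have near-normal humoral measures, while warning that subsets may respond poorly. At k = 0.7 the effect is small. That limits the magnitude but does not remove the ambiguity.

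**Conclusion.** The point holds as a flaw in a stated analysis rule. Adjusting for intensity cannot make survivors and the healthy reference comparable; it only selects the survivors to whom the ratio applies, and the plan specifies neither the level or mix nor the scale. At the 19% HCT share, a low-intensity reading multiplies the ratio by 1.07 to 1.26 and raises the per-comparison false-pass chance at a true 0.50 from about 0.3% to between about 1.5% and 20%. Equal weighting works the other way, and the observed mix is neutral for the point estimate. These sizes depend on the assumed k of 0.7 to 0.3, a log SD of 0.9, a two-level intensity scale, a fixed healthy GMT, and an HCT share taken from the eligible pool. The documents do not show that any particular level was intended or that a conclusion has been inflated.

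**What to change.** In section 8.2.2.1, make the unadjusted GMT ratio in each age-sex stratum the primary non-inferiority analysis. Label any intensity-adjusted ratio as sensitivity and standardise it to the observed survivor mix. Name one intensity scale for that purpose. Report ratios by HCT versus no HCT, and by ITR-2 level pooled over strata with age-sex-matched references, as descriptive secondary results. Keep intensity as a predictor in section 8.2.2.2.

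Pooling is needed because four ITR-2 levels in four strata make 16 cells; the 200 planned 9vHPV patients would average 200/16 = 12.5 per cell before exclusions. Even pooled, the subgroup estimates will be imprecise.

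The cost is SAP wording and a descriptive table, with no change to Table 7. There is some loss of precision if intensity explains titre variance: in the worked example the unadjusted log-scale SE is 0.120 against 0.106, about 13% wider. The change should be recorded as made after the January 2016 interim analysis of 133 qHPV patients, with its reason stated.
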